5.6.3.5 Electrocardiograms

Not applicable.

5.6.3.6 Other safety endpoints

5.6.3.6.1 Physical examinations

Physical examinations include general appearance; ears, nose, and throat; eyes, hair, and skin; and assessments of the respiratory, cardiovascular, gastrointestinal, musculoskeletal, hepatic, and neurological (including limb reflexes) systems, as well as mental status.

Clinically significant changes from Baseline in physical examination findings will be reported as AEs in the any TEAE table. Changes from Baseline in physical examination findings will therefore be summarized as part of the TEAE.

5.6.3.6.2 Growth assessment

Descriptive statistics for height and weight change from baseline will be reported by weight-categorized dose group over time. Growth percentiles will be calculated for height, weight, and body mass index (BMI) at Week 16, Week 64, and Week 124. A shift table of the number and percentage of participants falling in each percentile category from baseline to these post-baseline visits will be presented by weight-categorized dose group. The percentile categories are listed below.

- Height (percentile):
 - $<5^{\text{th}}$
 - $\geq 5^{\text{th}}$ to $<25^{\text{th}}$
 - $\geq 25^{\text{th}}$ to $<50^{\text{th}}$
 - $\geq 50^{\text{th}}$ to $<75^{\text{th}}$
 - $\geq 75^{\text{th}}$ to $<95^{\text{th}}$
 - ≥ 95
- Weight (percentile): the same percentile categories as height
- BMI (percentile):
 - $<5^{\text{th}}$ (underweight)
 - $\geq 5^{\text{th}}$ to $<85^{\text{th}}$ (normal or healthy weight)
 - $\geq 85^{\text{th}}$ to $<90^{\text{th}}$ (overweight)
 - $\geq 90^{\text{th}}$ to $<95^{\text{th}}$ (overweight)
 - $\geq 95^{\text{th}}$ to $<97^{\text{th}}$ (obese)
 - $\geq 97^{\text{th}}$ (obese)

Height and weight percentile reference levels are provided in Section 6.3.2.

5.6.3.6.3 Assessment and management of TB and TB risk factors

A summary of the number and percentage of participants with negative, positive, and indeterminate IGRA results at all applicable visits will be presented for the entire study.

A by-participant listing of the “Evaluation of signs and symptoms of tuberculosis” questionnaire data and IGRA results will be provided.

A by-participant listing of “All Treatment-Emergent Adverse Events Related to TB including latent TB and IGRA tests” will be provided. Please refer to Section 5.6.2.3.1 for additional information.

A by-participant listing of the result of chest x-ray for tuberculosis will be provided by weight-categorized dose group.

5.6.3.6.4 Pregnancy testing

A by-participant listing of the pregnancy test and outcome data will be provided by weight-categorized dose group at each timepoint for female participants.

5.7 Other Analyses

This section will outline PK and immunogenicity analyses.

5.7.1 Other endpoints and parameters

5.7.1.1 Pharmacokinetics

The primary variable of this study is plasma bimekizumab concentrations, assessed at Baseline, Week 1, Week 4, Week 8, Week 12, Week 16, Week 20, Week 40, Week 64, Week 88, Week 112, Week 124, EDV, and SFU Visit. Pharmacokinetic analyses will be performed in the PK-PPS. Summary tables will be created for the Initial Treatment Period for all participants in PK-PPS, and across All Periods (Initial Treatment Period + OLE Period) summaries for all participants that are in both the OLS and PK-PPS (i.e. all study participants who receive at least 1 dose of IMP at or after Week 20 in the OLE Period and who have at least 1 quantifiable plasma concentration without important protocol deviations that would affect the concentration in the OLE Period).

Bimekizumab plasma concentrations will be summarized with descriptive statistics and plotted for each weight-categorized dose group, at each scheduled visit. Summaries of bimekizumab plasma concentration over time will be reproduced with rounding to 1 decimal place and may be used for Plain Language Summaries. These tables and figures will be repeated by cumulative anti-bimekizumab antibody status (See Section 5.7.1.4.1.4) and by overall NAb status (See Section 5.7.1.4.2). Bimekizumab plasma concentrations summaries will be based on observed values, with each sample falling within the time window rules described below. No imputation will be used for missing data. If plasma concentration measurements are below the level of quantification (BLQ), then for calculation of the derived statistics the result will be set to $\frac{1}{2}$ of the LLOQ. Descriptive statistics including geometric mean, geometric coefficient of variation, and geometric mean 95% CI (if applicable) will be calculated if at least two-thirds of the values of interest are above the LLOQ and $n \geq 3$. If this is not the case, only median, minimum, and maximum will be presented.

All PK concentrations will be listed.

By-visit summaries and figures of plasma concentrations will exclude data points where protocol deviations and/or deviation from scheduled dose and sample collection window are expected to impact drug exposure. The protocol deviations will be reviewed by the Quantitative Clinical Pharmacology (QCP) representative and a decision about impacted data points will be made prior to generating summary statistics.

Out of window exclusion rules for bimekizumab plasma concentration summaries and figures:

- A sample will be considered out of window relative to the current dose and will be excluded from the summaries and graphs if the sample is collected >1 day after the dose administered at this visit. This excludes samples collected at an EDV visit, including Week 20 (if the participant did not enter the OLE Period) or Week 124 and Week 1, where a dose will not be administered at that visit.
- Alternatively, a sample will be considered out of window relative to the previous dose and will be excluded from the summaries and graphs if the sample is collected <14 days or >42 days after the previous dose, and the sample was collected prior to the dose at that visit (should a dose be scheduled). Week 1 will be excluded from this rule.

The PK data will be subject to a population PK analysis and will be described in a separate analysis plan and reported independently.

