4.1.4 Pharmacokinetics Per-Protocol Set

The Pharmacokinetics Per-Protocol Set (PK-PPS) will consist of all randomized participants who receive at least 1 dose of the IMP and provide at least 1 quantifiable plasma concentration post-dose without important protocol deviations that would affect the concentration. Pharmacokinetic variables will be analyzed for all participants in the PK-PPS and will be summarized as randomized.

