4.1.5 Open-label Set

The Open-label Set (OLS) will consist of all study participants who receive at least 1 dose of study medication at or after Week 20 in the OLE Period (including the Week 20 dose). The OLS will be the basis for analysis of data from OLE Period. OLS analyses will be based on the SS and as treated.

For summaries using both PK-PPS and OLS, participants will be summarized as randomized.

Immunogenicity analyses will be based on SS or OLS, and participants will be summarized as randomized.

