5.1.1.1.3 Study periods

The following study periods are defined for the classification by study period:

- Screening: visits with dates before randomization date
- Initial Treatment Period: from randomization date to Week 20 visit date
- OLE Period: From the date of Week 20 visit to the end of study. The Week 20 Visit date will serve as the start date of the OLE Period for participants who entered the OLE Period

The Week 20 Visit date serves, according to protocol, as both the end of the Initial Treatment Period and the beginning of OLE Period. Unless otherwise stated, any assessment or measurement made prior to or on the Week 20 visit will be attributed to the Initial Treatment Period (irrespective of time of collection), and adverse events related to dosing (see Section 5.6.2) and IMP administration will be attributed to the OLE Period.

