5.1.1.7.2 PK and antibody missing data

Pharmacokinetic analyses, including those of the primary PK outcome, will be based on observed data; no data will be imputed. If plasma concentration measurements are below the lower limit of quantification (LLOQ), then for calculation of the derived statistics the result will be set to half of the LLOQ.

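### The bracket explaining the All-Periods PK set in SAP 5.7.1.1 adds an OLE condition that neither OLS nor PK-PPS contains; on one reading it drops participants whose OLE levels are all below quantification

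*SAP*

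**What the plan says.** SAP 5.7.1.1 plans two sets of concentration summaries. For the first, "Summary tables will be created for the Initial Treatment Period for all participants in PK-PPS". The second, across the Initial Treatment Period and the OLE, consists of "summaries for all participants that are in both the OLS and PK-PPS". A bracket then explains the second set as participants dosed in the OLE "who have at least 1 quantifiable plasma concentration without important protocol deviations that would affect the concentration in the OLE Period".

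The two component sets are defined in SAP 4.1:

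- PK-PPS (4.1.4): randomized, dosed at least once, and able to "provide at least 1 quantifiable plasma concentration post-dose without important protocol deviations that would affect the concentration". Protocol 9.1 has the same condition. Neither names a study period.
- OLS (4.1.5): participants who "receive at least 1 dose of study medication at or after Week 20 in the OLE Period (including the Week 20 dose"). There is no concentration requirement.

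Three other rules bear on the point:

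- SAP 5.1.1.1.3: "any assessment or measurement made prior to or on the Week 20 visit will be attributed to the Initial Treatment Period".
- SAP 5.1.1.7.2, for a concentration below the LLOQ: "then for calculation of the derived statistics the result will be set to half of the LLOQ". Section 5.7.1.1 repeats this.
- SAP 5.7.1.1: the geometric mean and related statistics "will be calculated if at least two-thirds of the values of interest are above the LLOQ" and there are at least 3 values.

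SAP 6.2, which lists departures from the protocol's analyses, mentions summaries using PK-PPS and OLS together but no OLE-specific concentration requirement.

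**The concern.** A bracket that explains an overlap should describe that overlap, and this one does not. Someone programming from Section 4.1 and someone programming from the bracket could produce different denominators for the same table.

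On the reading that requires a quantifiable OLE concentration, the set is also selected on the variable it summarises. A participant with no quantifiable value in the OLE would leave the All-Periods tables altogether, although the half-LLOQ rule exists to keep such results in. Their Initial Treatment Period values would leave those tables too.

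The summaries are by weight-categorized dose group and are repeated by cumulative ADAb status and overall NAb status. With about 20 participants per arm these cells are small, and the antibody repeats are where a fall in exposure would be looked for. The All-Periods immunogenicity tables use the whole OLS (SAP 5.7.1.4), so the two families of tables could describe different people.

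**Working it through.** **No figure to reproduce.** No number in the plan depends on this set. The total of 40 comes from simulations whose inputs are not given, and the analyses are descriptive.

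**Step 1. Compare the sets.**

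- Named overlap: dosed at or after Week 20, and at least one quantifiable post-dose concentration in any period, subject to the PK-PPS deviation condition.
- Bracket, reading 1 (the closing words govern the concentration): dosed at or after Week 20, and at least one quantifiable concentration in the OLE.
- Bracket, reading 2 (the closing words govern the deviations): dosed at or after Week 20, at least one quantifiable concentration at any time, and no important deviation affecting OLE concentrations.

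Reading 1 can be narrower than the overlap. The Week 20 sample belongs to the Initial Treatment Period and the next scheduled one is at Week 40. A participant quantifiable up to Week 20 and BLQ at every later sample is in both OLS and PK-PPS but fails reading 1. Reading 2 removes nobody for being BLQ, but it could admit someone whose important deviation affected only Initial Treatment Period concentrations. Neither reading equals the overlap.

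**Step 2. Direction under reading 1.** Removed participants would have entered each OLE visit at half the LLOQ, below every quantifiable value. Removing them cannot lower an OLE-visit mean. For Initial Treatment Period visits shown in the same tables the direction is not fixed.

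**Step 3. Size under reading 1 (illustration).** The documents give no LLOQ, concentrations or BLQ rate, so all inputs here are assumptions:

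- n = participants with a value at the visit in the true overlap: 20 (a full dose group) or 10 (a weight-categorized group).
- k = those among them whose OLE values are all BLQ. The rest are taken as quantifiable.
- R = geometric mean of the quantifiable values divided by half the LLOQ: 5, 20 or 100, that is 2.5, 10 or 50 times the LLOQ.

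With M the geometric mean of the quantifiable values, the restricted set gives M and the overlap gives M^((n−k)/n) × (LLOQ/2)^(k/n). The ratio of restricted to overlap is R^(k/n).

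| n | k | R = 5 | R = 20 | R = 100 |
|---|---|---|---|---|
| any | 0 | 1.00 | 1.00 | 1.00 |
| 20 | 1 | 1.08 | 1.16 | 1.26 |
| 20 | 3 | 1.27 | 1.57 | 2.00 |
| 10 | 1 | 1.17 | 1.35 | 1.58 |
| 10 | 2 | 1.38 | 1.82 | 2.51 |

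For the arithmetic mean the ratio is 1/[(n−k)/n + (k/n)/R]. With n = 20 and k = 1 it is 1.04 to 1.05.

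**Step 4. The two-thirds rule.** With 7 of 20 all-BLQ, 13/20 = 65% of values are above the LLOQ and the overlap shows no geometric mean. The restricted set would show one from the remaining 13. With 4 of 10, 6/10 = 60%, and the same switch occurs with 6 left. These are extreme cases.

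**Step 5. Chance that it arises at all.** For a per-person probability p of having only BLQ values in the OLE, the chance of at least one among 40 is 1 − (1 − p)^40: 18%, 33%, 55% and 87% for p = 0.5%, 1%, 2% and 5%. These p are assumed, and 40 supposes that everyone enters the OLE.

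**The case against.** The best defence is that this is a loose gloss on two sets already defined. The named overlap should govern, and the closing words can attach to the nearest noun, so that they limit only which deviations count. That stands as a possible reading. It does not rescue the text, because that reading also departs from the PK-PPS and the two readings give different sets.

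The practical effect may be nil. Protocol 2.3 says both regimens permit quantification of plasma concentrations. OLE entry requires an IGA of 2 or less at Week 20, and dosing continues every 4 weeks. This makes participants with only BLQ values less likely but does not exclude them; the Protocol 2.3 statement accompanies a reference to tolerability in adults and does not address antibody-related loss.

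A reader might infer that the clause removes participants who lose exposure over time and so hides the loss. The documents do not support that in general. One quantifiable OLE value keeps a participant in, and samples are planned at Weeks 40, 64, 88, 112 and 124, at early discontinuation and at safety follow-up. Someone quantifiable at Week 40 and BLQ afterwards stays, with the later values at half the LLOQ. Only a participant unquantifiable at every OLE sample, or with no OLE sample, is at issue. Those without an OLE sample add nothing to OLE-visit means; what is lost is their earlier values in the All-Periods tables, with no fixed direction of bias.

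**Conclusion.** The point holds as a definitional inconsistency of minor severity. The bracket adds a condition found in neither set definition, is ambiguous, and matches the named overlap on neither reading. On the reading that requires a quantifiable OLE concentration, it bypasses the half-LLOQ rule for participants with the lowest OLE exposure and can inflate the All-Periods tables and figures, including the antibody repeats.

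The size is unknown and may be zero. The illustrated rises of 8% to 26% for 1 of 20 and 17% to 58% for 1 of 10 rest entirely on the assumed R, n and k.

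It would be tempting to conclude that the primary variable is inflated. That goes too far. Initial Treatment Period summaries use the full PK-PPS and all concentrations are listed. Population PK has its own plan (SAP 5.7.1.1). PS0021 dosing is to be determined from data assessed up to completion of the Initial Treatment Period (Protocol 9.7.1; SAP 5.1 and 5.9). Neither of these last two is shown to use the disputed set.

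**What to change.** In SAP 5.7.1.1, delete the closing words *in the OLE Period* from the bracket, so that the set is the plain overlap of OLS (4.1.5) and PK-PPS (4.1.4). State that participants with only BLQ values in the OLE stay in the All-Periods summaries at half the LLOQ under 5.1.1.7.2.

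If a separate OLE concentration set is intended, define it in Section 4.1, list it in Section 6.2 and say there whether participants with only BLQ OLE values are kept.

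The cost is one phrase and the matching analysis-set flag. No new data are needed.

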9.3 Planned efficacy/outcome analyses

9.3.1 Analysis of the primary endpoint

9.3.1.1 Pharmacokinetic analyses

The primary variable of this study is bimekizumab plasma concentrations, which will be summarized by visit and dose group and presented together with descriptive statistics for the PK-PPS. Concentrations will be plotted for the overall population and for each dose group, and by treatment-emergent anti-bimekizumab antibody titer if appropriate. Objectives and endpoints related to PK analyses are described in Section 3.

A population PK analysis will be performed to derive the population estimates of PK parameters such as clearance and volume of distribution. This analysis will be performed by combining the data from the current study with data from relevant adult studies to evaluate the effect of body weight or other body size covariates on PK parameters. The model developed, including covariate effects, will be used to predict the PK and dosing for pediatric participants from 6 to <18 years of age in the Phase 3 study (PS0021). Further details on the modeling can be found in the Modeling and Simulation Plan.

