- Overall negative, if the study participant has all samples reported as negative or has only one missing/inconclusive sample.
- Overall missing, if the study participant has more than one missing ADA b sample for any reason (eg, insufficient sample, ADA b sample status is inconclusive, no result is available or a missed scheduled collection) and all other available ADA b samples are negative.

5.7.1.4.1.3 ADA b Subcategories

Furthermore, the following subcategories for each participant will be derived:

1. **Pre ADA b negative – treatment-emergent ADA b negative (category 1):** Includes participants who are negative at Baseline and ADA b negative at all sampling points posttreatment (excluding SFU) or has only one postbaseline missing/inconclusive sample. This includes study participants who have a missing/inconclusive sample at Baseline with all post-treatment samples reported as ADA b negative.
2. **Pre ADA b negative – treatment-emergent ADA b positive (category 2):** Includes participants who are negative at Baseline and ADA b positive at any sampling point posttreatment (excluding SFU). This group also includes participants who have a missing/inconclusive sample (either missing or insufficient volume) at Baseline with 1 or more ADA b positive posttreatment samples.
3. **Pre ADA b positive – treatment-emergent reduced ADA b (category 3):** Includes participants who are positive at Baseline, and ADA b negative at all sampling points posttreatment (excluding SFU) or has only one post-Baseline missing/inconclusive sample.
4. **Pre ADA b positive – treatment-emergent unaffected ADA b positive (category 4):** Includes participants who are positive at Baseline and are positive at any sampling point posttreatment (excluding SFU) with titer values of the same magnitude as Baseline (ie, < 2.07-fold difference from the Baseline value; 2.07 being the validated minimum significant ratio for this assay method).
5. **Pre ADA b positive – treatment-emergent ADA b boosted positive (category 5):** Includes participants who are positive at Baseline and are positive at any sampling point post treatment (excluding SFU) with increased titer values compared to Baseline (≥ 2.07 -fold difference increase from Baseline).
6. **Inconclusive (category 6):** Includes participants who have a positive Baseline sample, and some posttreatment samples are missing/inconclusive, while other posttreatment samples are ADA b negative.

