7. **Total treatment-emergent (category 7 [categories 2 and 5 combined]):** Includes study participants who are preADA b negative – treatment emergent ADA b positive (category 2) and preADA b positive – treatment boosted ADA b positive (category 5).
8. **Total prevalence of preADA b positivity (category 8 [categories 3, 4, 5, and 6 combined]):** Study participants that are tested ADA b positive at Baseline.
9. **Missing (category 9):** Includes participants who are antibody negative at Baseline and have more than 1 post-treatment scheduled assessments reported as missing/inconclusive, while other samples are ADA b negative. Note this is also applicable to participants who have a

missing Baseline sample, at least one missing/inconclusive postbaseline sample and have no ADAb positive samples.

Derivation for above classification will be different for the Initial Treatment Period (SS) and the combined Initial Treatment and OLE Periods (OLS). For the Initial Treatment Period, no OLE or SFU data will be considered. For the combined Initial Treatment and OLE Periods, data from the OLE and SFU visits be considered. That is, each instance of “excluding SFU” in the categories above, should be changed to “including SFU.”

In the case that a sample is collected 1 or more days following the scheduled visit date in which the drug was administered, the ADAb results for that sample will be associated with the scheduled visit and summarized accordingly. Such samples will also be considered when ADAb results are summarized over a given study period.

5.7.1.4.1.4 Cumulative ADAb status groups for PK summaries

The ADAb status (positive, negative or missing) will be considered in a cumulative manner at each time point for the PK summaries.

A study participant will be counted positive from the first visit at which the study participant achieved a positive ADAb sample result to the end of the treatment period, regardless of any missing/inconclusive or negative ADAb sample result.

If a study participant has only negative ADAb samples or only one missing/inconclusive sample with all negative ADAb samples up to that timepoint, the study participant will be classified as negative. An exception remains for the Baseline Visit where only one sample could be available. If the sample is missing/inconclusive, then the sample will be classified as being negative for the cumulative ADAb status.

Otherwise, the study participant will be classified in the missing ADAb category.

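### The SAP's antibody split of the concentration outputs pools pre-existing with treatment-emergent antibody, where the protocol planned a treatment-emergent view, and the change is not declared

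*SAP*

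**What the plan says.** Protocol 9.3.1.1 names the plasma concentrations as the primary variable, "which will be summarized by visit and dose group and presented together with descriptive statistics for the PK-PPS". That summary has no antibody split. Antibody enters only in the plots, which are to be shown overall, by dose group, and "by treatment-emergent anti-bimekizumab antibody titer if appropriate".

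SAP 5.7.1.1 summarizes and plots concentrations by weight-categorized dose group and visit, and then states: "These tables and figures will be repeated by cumulative anti-bimekizumab antibody status". It also repeats them by overall neutralizing-antibody (NAb) status.

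SAP 5.7.1.4.1.4 defines the cumulative status: "A study participant will be counted positive from the first visit at which the study participant achieved a positive ADAb sample result" and this label holds "to the end of the treatment period, regardless of any missing/inconclusive or negative ADAb sample result". Baseline lies inside the rule, because a missing Baseline sample has its own provision: "An exception remains for the Baseline Visit where only one sample could be available".

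SAP 5.7.1.4.1.3 separates the kinds of antibody history. Category 3 is the participant whose antibody disappears: "Includes participants who are positive at Baseline, and ADA b negative at all sampling points posttreatment". Category 4 is Baseline-positive with no meaningful change in titer. Category 5 is Baseline-positive with a titer rise of at least 2.07-fold. The SAP also defines a combined group, "Total treatment-emergent (category 7 [categories 2 and 5 combined", but does not use it for the by-visit concentration outputs.

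**The concern.** The question of interest is whether antibody raised by bimekizumab goes with lower exposure. The protocol's qualifier points at that question. The cumulative status answers a different one, whether the participant has had any positive sample so far, including one taken before the first dose. A single positive Baseline sample fixes the label through the treatment period, even if every later sample is negative.

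If pre-existing reactivity has little effect on clearance, mixing it into the positive group pulls the positive-to-negative ratio towards 1 and makes a real effect of treatment-emergent antibody harder to see. A reader who compares the report with the protocol would also find no note that the grouping had changed or that titer had been dropped from the grouped concentration outputs.

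**Working it through.** No figure in the plan is at stake, so the check is a comparison of the text followed by an illustration on assumed inputs.

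**Text comparison**

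| Category (SAP 5.7.1.4.1.3) | Treatment-emergent? | Cumulative status during treatment |
|---|---|---|
| 2: negative (or missing) at Baseline, positive later | Yes | Positive from first positive sample |
| 3: positive at Baseline, negative later | No | Positive from Baseline on |
| 4: positive at Baseline, not boosted | No | Positive from Baseline on |
| 5: positive at Baseline, boosted | Yes | Positive from Baseline on, so also before the boost |
| 6: positive at Baseline, later samples negative or missing | No | Positive from Baseline on |

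- The NAb split does not fill the gap. SAP 5.7.1.4.2 classifies NAb status on Baseline and post-Baseline results together.
- The efficacy grouping in SAP 5.7.1.4.1.5 does leave Baseline out when it counts positive samples, and SAP 5.7.1.4.1.6 uses category 7 for first-occurrence tables. The SAP gives no reason for treating concentrations differently.
- SAP 6.2 lists changes such as LOCF in place of multiple imputation and the PK set being summarized as randomized. It does not list this one.

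**Size, if pre-existing antibody is inert.** Let r be the true ratio of geometric mean concentrations (treatment-emergent positive to never positive), and f the share of the cumulative-positive group that is Baseline-positive and not boosted. If those participants have ratio 1, the observed ratio is r^(1−f). The documents give no value for f or r, so both are assumptions.

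| True r | f = 10% | f = 30% | f = 50% |
|---|---|---|---|
| 0.50 | 0.50^0.9 = 0.54 | 0.50^0.7 = 0.62 | 0.50^0.5 = 0.71 |
| 0.70 | 0.70^0.9 = 0.73 | 0.70^0.7 = 0.78 | 0.70^0.5 = 0.84 |

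**Does the direction depend on the assumption?** Take 20 participants in a dose group (Protocol 4.1). Assume m = 6 treatment-emergent positives with ratio g = 0.50, and b = 2 Baseline-positive, non-boosted participants with ratio h, each relative to never-positive participants.

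- Cumulative split: exp[(m ln g + b ln h)/(m + b)].
- Treatment-emergent against everyone else: exp[ln g − b ln h/(20 − m)].
- Treatment-emergent against never positive, third group kept apart: g.

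| Pre-existing antibody | Cumulative | Emergent vs everyone else | Emergent vs never positive |
|---|---|---|---|
| Inert (h = 1) | 0.50^(6/8) = 0.60 | 0.50 | 0.50 |
| Equally active (h = 0.50) | 0.50 | 0.50 × 0.50^(−2/14) = 0.55 | 0.50 |
| Nobody Baseline-positive (b = 0) | 0.50 | 0.50 | 0.50 |

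Over m = 4 to 8 and b = 1 to 4 with equally active antibody, the emergent-versus-everyone-else split shows 0.52 to 0.63 for a true 0.50, and 0.72 to 0.79 for a true 0.70. Each two-group split can therefore mislead under one assumption. The three-group display gives the right emergent contrast under all three.

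**The case against.** The case for leaving the plan alone is substantial.

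- **The protocol did not commit to an antibody split of the primary summary.** A reader might infer that the SAP replaced one. It did not: the protocol item is a conditional plot by titer, and the summary by visit and dose group stands. This point holds, and it limits the matter to supportive, descriptive outputs.
- **The distinction is not wholly lost.** A reader might infer that nothing else in the plan shows treatment-emergent antibody against concentration. SAP 5.7.1.4.1.6 plans individual plots of concentration, titer and PASI90 response grouped by subcategory, which separate categories 2 to 5. This also holds. Those plots are participant-level, however, and give no group geometric mean or interval.
- **Dilution is not established.** It needs Baseline-positive, non-boosted participants to exist and their antibody to have little effect on clearance. The documents show neither, and category 4 participants remain antibody-positive on treatment. This is correct, so the size can only be given conditionally.
- **The PS0021 dose.** A reader might infer that the blurred split feeds the dose choice. Protocol 9.3.1.1 and 9.3.3 derive the dose from population PK and exposure-response modeling described in separate plans. No passage names the antibody-stratified concentration table as an input.
- **Every visit.** A reader might take the positive label to cover all visits. The rule runs to the end of the treatment period and does not state the status at Safety Follow-up.
- **Small groups.** A further split of about 20 participants per dose group will often be sparse. That is a reason to show it at Dose A and Dose B level. It does not justify pooling unlike participants.

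**Conclusion.** The mismatch is real and can be read directly from the text. The protocol planned a treatment-emergent view of concentrations. The SAP's grouped outputs use a status that includes Baseline and carries it forward, the NAb split does the same, and SAP 6.2 is silent.

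The consequence is conditional. With inert pre-existing antibody making up 10% to 50% of the positive group, a true ratio of 0.50 appears as 0.54 to 0.71, and 0.70 as 0.73 to 0.84. With equally active pre-existing antibody, or with nobody positive at Baseline, the cumulative split is not diluted. The stronger reading, that the SAP necessarily hides an antibody effect on exposure, is not supported. The main primary summary is untouched, and the individual plots keep part of the distinction. The change is still worth making, because the SAP already derives the categories needed and the three-group display is right under each of these assumptions.

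**What to change.** In SAP 5.7.1.1 and 5.7.1.4.1.4, add a concentration table and figure by treatment-emergent status (category 7), or by treatment-emergent titer as the protocol planned. Present it at Dose A and Dose B level with three groups:

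- never positive;
- treatment-emergent (categories 2 and 5);
- Baseline-positive and not boosted, including participants whose boost cannot be judged because a titer is missing.

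Do not pool the third group with the negatives. State whether a participant is placed by the category reached over the period or from the first post-Baseline visit that meets the criterion. Categories 2 and 5 are defined over a period, so the second option needs one new visit-level flag. Keep the cumulative version as supportive, and list the change of grouping, including the loss of titer, in SAP 6.2.

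The cost is SAP wording, one grouping variable and one extra descriptive output. Some groups will fall below the SAP's minimum of n ≥ 3 for geometric means and will show only median, minimum and maximum.
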